9.5 STUDY SIZE

9.5.1 Determination of sample size (LEMTRADA exposed)

The sample size of approximately 204 women exposed to LEMTRADA during pregnancy (prospective) is expected to achieve approximately 193 women followed up to 1 year post-delivery, allowing approximately 5% of recruited women to have missing pregnancy outcome data. With this sample size and a sample size of 117 in the comparator group, at 80% power and a 1-sided two-sample test with significance level of 0.025, we will be able to detect a 2.0-fold higher relative risk for a background spontaneous abortion rate of 13.5%, which encompasses the likely risk range for spontaneous abortions amongst women in the reference cohorts. In the reference cohorts of pregnancies from women with and without MS who were not exposed to LEMTRADA, where the rates of spontaneous abortion is expected to be 16.6% for women without MS (3) and 11.5% - 19.5% for women with MS (4,5,6). Retrospective pregnancies are not part of this sample size calculation and are collected additionally.

Table 1 shows the type of differences that may be detected comparing LEMTRADA-exposed pregnancies with various background rates for spontaneous abortion and any birth defects. For purposes of sample size calculation, a combination of general population background rates and rates published in the literature for women with MS with pregnancies unexposed to disease-modifying therapy were used.

16-Nov-2016 Version number: 1

Table 1 - Sample Size and Detectable Effect Size for Selected Endpoints

Endpoint	Population	Background Rate	Total Sample size	RR
Spontaneous abortion	General population	16.6% (3)	204 (Effective 193)	1.86
	Women with MS	11.5% (5)	204 (Effective 193)	2.12
	Women with MS	19.5% (4)	204 (Effective 193)	1.77
	Background Comparator Groups	13.5%	204 (Effective 193)	2.0
Any major birth defect General population		3% (8,9)	204 (effective 154)	4.05
	Women with MS	3% (10)	204 (effective 154)	4.05

RR: Relative Risk.

Sample size calculations were performed using EAST software version 6.2.

Assuming 5% drop out (outcome unavailable): 204*95%=193 patients will permit detection of RR=2.0 for a background rate of 13.5% with 80% power and 0.025 significance level based on 1-sided two sample Fisher's exact test (with comparator group sample size =117)

Assuming 80% live birth, 193*80%=154 live births.

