9.6.2 Data collected

9.6.2.1 Date collected from the mother (patient) by Health Care Provider (HCP)

Once patients sign the informed consent, patients' enrollment and follow up information are collected by the HCP. Whenever permitted in local legislation, signature of ICF will mean that the pregnant patient consents that medical records of herself and of the infant can be released by the HCP to the NC for further use in this Registry. After the ICF is signed, the enrolment interview can be done by HCP or registry staff if the HCP is not available; follow-up interviews can be done by phone or in person (by HCP or registry staff). Forms with patients' data completed by the HCP are sent to the National Coordinator by mail, fax, or email (on a secure server). Upon receipt, the National Coordinator reviews the forms for completeness, queries the HCP for missing data, and de-identifies and key-codes all forms before entering them into the CRF. Information to be collected during maternal interviews includes:

- Demographics: maternal age, maternal race/ethnicity (as per local regulations), education, family income category.
 - Of note: Patient race or ethnicity (e.g., "Caucasian/White, Black, Asian/Oriental, Others" will be collected in this study because these data are required by several regulatory authorities (e.g., on afro American population for Food and Drug Administration (FDA), on Japanese population for the PMDA in Japan, or on Chinese population for the CFDA in China)"
- Targeted medical history including prior treatment for MS.
- History of previous pregnancies and outcomes of each:
 - Pregnancy outcome: live birth, stillbirth, spontaneous abortion, induced abortion,
 - Pregnancy complications,
 - Fetal/neonatal abnormalities and type.
- Current pregnancy: fertility treatments (if applicable), date of last menstrual period, expected delivery date, prenatal tests conducted and results, pregnancy status.
- Risk factors: Smoking, alcohol use, illicit drug use, pre-pregnancy BMI
- LEMTRADA exposure (infusion dates).
- Concomitant medications including over-the-counter and prescription medications, vitamin supplements including folic acid, herbal medicines from one month prior to the date of enrollment.
- At pregnancy completion (as applicable depending on pregnancy outcome)
 - Pregnancy outcome (live birth, spontaneous abortion, stillbirth, induced abortion) and type (singleton or multiple),
 - For live births.

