9.7.4 Analysis variables

Definitions of pregnancy outcomes are consistent with, but not limited to, definitions used by the Center for Disease Control and Prevention Metropolitan Atlanta Congenital Defects Program (CDC MACDP), the National Center for Health Statistics (NCHS), and Organization of Teratology Information Specialists (OTIS) (2,11). Overall pregnancy outcome will be classified into one of the following mutually exclusive categories: spontaneous abortions, induced abortions/elective terminations, stillbirth, preterm birth and live birth. Every birth defect identified in a live birth will be classified into major or minor congenital malformation.

Other outcomes of interest are: minor congenital malformations, preterm birth, small for gestational age at birth, and any other adverse pregnancy outcomes. The study will endeavor to assess all pregnancy outcomes for the presence of malformations and functional deficit in the infant up to 1 year of age. A detailed description of pregnancy outcomes is provided in Appendix A.

Additional analysis variables such as maternal age, smoking status during pregnancy, and maternal comorbidities may be included in analyses as important confounders or in subgroup analyses. These additional variables will be fully described in a separate statistical analysis plan which will be developed and finalized prior to database lock.

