9.7.4.1 Main criteria

Main criterion is rate of spontaneous abortion in the prospectively collected LEMTRADA-exposed group versus comparison cohorts of pregnancies from women with and without MS who were not exposed to LEMTRADA. Descriptive statistics of maternal and pregnancy characteristics and the timing of exposure will be provided for retrospectively collected cases of spontaneous abortions to qualitatively describe this patient population.

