9.7.4.3 Criteria obtained from comparison cohorts

The following comparison groups in the AUBAGIO® (teriflunomide) North American pregnancy exposure registry (Genzyme study OBS13499) will be used:

- Cohort II (North American AUBAGIO Pregnancy Outcome Exposure Registry Cohort II) -pregnant women with MS not exposed to AUBAGIO during the current pregnancy modified to also exclude women exposed to LEMTRADA
- Cohort III (North American AUBAGIO Pregnancy Outcome Exposure Registry Cohort III) pregnant women without MS and not exposed to AUBAGIO during the current pregnancy modified to also exclude women exposed to LEMTRADA

NOTE: Cohort I (pregnant women with MS exposed to AUBAGIO) are excluded

Patient-level data from the AUBAGIO pregnancy registry are made available to the sponsor (Genzyme, a Sanofi Company) when data has been stripped of personal identifiers.

Following variables will be collected:

- Maternal age
- Maternal race/ethnicity
- Socioeconomic status
- Prior pregnancy history: gravidity/parity and previous outcomes
- Periconceptional use of folic acid containing supplements
- Unintended pregnancy
- Gestational age at enrollment
- Exposure to other medications (including known teratogens) and other MS medications
- Comorbidities
- Disease severity measure(s)

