9.7.5 Statistical methods

Endpoints are prospectively collected rates of spontaneous abortion, major and minor congenital malformations, stillbirth, elective terminations, preterm birth, small for gestational age at birth, and any other adverse pregnancy outcomes for women exposed to LEMTRADA during pregnancy.

All the comparisons below between women exposed to LEMTRADA during pregnancy (prospectively collected) and unexposed comparison groups will be carried out separately against each comparison group.

Rates and 95% CI will be calculated. Rates will be compared between women exposed to LEMTRADA during pregnancy (prospective) and women in unexposed comparison groups by calculating the relative risk (RR) and its 95% CIs. As the majority of the events rates are anticipated to be low, when applicable, comparisons will be conducted using exact statistical methods.

A supportive analysis of (prospective) spontaneous abortion as a time-to-event endpoint will be conducted using the Kaplan-Meier method adjusting for left-truncation. If data are available, propensity score matching and covariate adjustment may be used in the Cox regression context with left-truncation to adjust for potential confounding factors, such as gestational age at enrollment, comorbidities, prior birth defects/abnormalities, exposure to other medications, etc.

For other endpoints (prospective), if data are available, propensity score matching and covariate adjustment may also be used in the logistic regression context to adjust for potential confounding factors. These approaches will reduce the influence of risk modifiers in determining the event risk ratio between Lemtrada-exposed women and non-Lemtrada-exposed women.

Qualitative descriptive statistics on maternal and pregnancy characteristics and the timing of LEMTRADA exposure will be provided for the retrospectively collected pregnancy cases.

Additional supportive analyses will be documented in the statistical analysis plan (SAP).

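### The main spontaneous-abortion RR is unadjusted, although maternal age and previous pregnancy outcomes are held for exposed women and for Cohorts II and III

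*Protocol*

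**What the plan says.** Protocol 9.7.4.1 sets the primary comparison: "Main criterion is rate of spontaneous abortion in the prospectively collected LEMTRADA-exposed group versus comparison cohorts of pregnancies from women with and without MS". Section 9.7.5 carries it out as an RR with 95% CI, separately against each comparison group and with exact methods when applicable. The sizing in 9.5.1 is also unadjusted: a "1-sided two-sample test with significance level of 0.025", identified under Table 1 as Fisher's exact test.

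For spontaneous abortion, 9.7.5 places adjustment in a supportive time-to-event analysis and makes it conditional on data being available: "propensity score matching and covariate adjustment may be used in the Cox regression context with left-truncation to adjust for potential confounding factors". The factors given as examples are gestational age at enrolment, comorbidities, prior birth defects or abnormalities, and other medications. The list is left open. Logistic adjustment is offered only for the other endpoints.

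Section 9.7.4 adds: "Additional analysis variables such as maternal age, smoking status during pregnancy, and maternal comorbidities may be included in analyses as important confounders". It leaves the full description to the SAP.

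On data, 9.6.2.1 collects maternal age in exposed women and, for each previous pregnancy, "Pregnancy outcome: live birth, stillbirth, spontaneous abortion, induced abortion". For Cohorts II and III, 9.7.4.3 lists maternal age and "Prior pregnancy history: gravidity/parity and previous outcomes", and says that de-identified patient-level data reach the sponsor.

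**The concern.** Exposed and comparison women come from different registries, and nothing in the design balances them. A crude RR therefore mixes any drug effect with differences in age and pregnancy history. Previous spontaneous abortion is the history counterpart of the primary outcome, yet 9.7.5 names prior birth defects as an adjustment factor and does not name prior loss.

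The protocol recognises the general problem: 9.7.5 says that adjustment reduces the influence of risk modifiers. It still leaves its main estimate for the primary outcome without that protection. Data availability does not explain the choice, because 9.6.2.1 and 9.7.4.3 put both kinds of variable on both sides of the comparison with Cohorts II and III. At stake is a raised RR that reflects who enrolled, or a real increase that is hidden. Deciding on adjustment after the crude RR is known would also weaken whichever result is reported.

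**Working it through.** **Inputs from the protocol (9.5.1, 9.5.2).** Exposed n = 204 × 0.95 = 193.8, taken as 193. Comparator n = 125 × 0.96 × 0.98 = 117.6, taken as 117. Background rate 13.5%; RR 2.0, so 27.0% in exposed women; one-sided 0.025.

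**The plan's own figure.** The protocol states that "204*95%=193 patients will permit detection of RR=2.0 for a background rate of 13.5% with 80% power and 0.025 significance level". Enumerating both binomials under the one-sided Fisher test gives a power of 78.1%; the pooled normal approximation gives 81.3%. Both lie within 2 points of 80%, so the stated power reproduces. With no effect and no imbalance, the Fisher test rejects in 1.7% of cases.

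**Assumptions (not in the protocol).** A risk factor has RR r = 1.5 to 2.0 for spontaneous abortion. Its prevalence is 20% in comparators and 25% or 35% in exposed women. In the last scenario two such factors act independently and in the same direction.

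**Formula.** Crude RR with no drug effect: b = [1 + pE(r − 1)] / [1 + pU(r − 1)], where pE and pU are the prevalences in exposed and unexposed women.

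- 5 points, one factor: r = 1.5 gives 1.125/1.10 = 1.02; r = 2.0 gives 1.25/1.20 = 1.04.
- 15 points, one factor: r = 1.5 gives 1.175/1.10 = 1.07; r = 2.0 gives 1.35/1.20 = 1.125.
- 15 points, both factors: 1.068² = 1.14; 1.125² = 1.27.

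**Effect on the sizing test.** For false signals the exposed rate is 13.5% × b. For power under the reversed imbalance it is 27.0% / b. The comparator rate stays at 13.5%.

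| Imbalance | Crude RR, no drug effect | One-sided Fisher rejection, no drug effect | Power at true RR 2.0, imbalance reversed |
|---|---|---|---|
| None | 1.00 | 1.7% | 78% |
| 5 points, one factor | 1.02–1.04 | 2.0–2.3% | 74–71% |
| 15 points, one factor | 1.07–1.13 | 2.9–4.2% | 66–56% |
| 15 points, both factors | 1.14–1.27 | 4.7–9.7% | 54–35% |

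**Can two covariates be supported?** Expected events are 310 × 0.135 = 42 with no effect, and 193 × 0.27 + 117 × 0.135 = 68 at RR 2.0. That is enough for a model with exposure and these two factors.

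**The case against.** The strongest reply is that covariate choice belongs to the SAP, which is not at hand. Section 9.7.4 already names maternal age as a possible important confounder and does not confine it to supportive analyses. The factor list in 9.7.5 is open-ended and excludes neither age nor prior loss. This stands against any complaint that the list is incomplete. It does not answer the point made here, which is which estimate is the main one: neither 9.7.4 nor 9.7.5 says that the SAP will replace the crude RR.

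A second reply is that 9.7.5 reports RRs with confidence intervals and sets no testing rule. That is correct. The one-sided Fisher test belongs to the sizing, so the rejection rates above are a yardstick and not the error rate of a planned decision. Section 9.9 also warns that volunteers may be particularly high- or low-risk pregnancies, although it does not discuss imbalance between the groups in these two factors.

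Third, the size rests wholly on assumptions. A 5-point imbalance in one factor leaves the false-signal rate below the nominal 2.5%. This stands too.

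A reader might infer that the protocol's primary RR is biased, or that an imbalance will be read as a drug effect. The documents do not support that: they give no covariate distributions, no risk-factor effects and no rule that turns the RR into a conclusion.

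**Conclusion.** The point holds in a limited form. The main spontaneous-abortion estimate is crude, adjustment for that outcome is optional and supportive, and the variables needed for a better estimate against Cohorts II and III are already collected. The weakness is clearer for previous spontaneous abortion, never named as an adjustment factor, than for maternal age, which 9.7.4 mentions.

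The distortion could be negligible or material. Under the assumptions shown it runs from a crude RR of 1.02 up to 1.27 with no drug effect; the upper end needs 15-point imbalances in both factors in the same direction. The stated sample size is not in error. The point does not extend to EUROCAT or MACDP, for which the protocol documents no such patient-level variables. The case rests on reducing bias, since the gain in precision would be small.

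**What to change.** In 9.7.5, for Cohorts II and III only, prespecify as the main spontaneous-abortion estimate an RR adjusted for maternal age and previous spontaneous abortion, for example by modified Poisson regression with robust errors or by standardisation. Report the crude RR alongside.

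In the supportive left-truncated Cox analysis, make adjustment mandatory and name both factors. That model should stay, because it also handles delayed entry, which an adjusted RR on simple proportions does not do by itself.

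The cost is protocol and SAP wording and one further model, with no new data collection. Two practical matters need settling before database lock. Women with missing pregnancy history need an unknown category or imputation. The level of detail behind the previous-outcomes item in Cohorts II and III must be confirmed, since 9.7.4.3 does not say that spontaneous abortions are recorded separately.

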9.8 QUALITY CONTROL

9.8.1 Data collection, validation and data quality control at MAH representative level

Data will be collected by the HCPs, providing care to the woman and/or infant, as applicable. Data recorded from interviews or abstracted from medical records are considered the primary data sources for this study and will be retained and reported to National Coordinator by the HCP. Subsequently data will be entered into a study-specific database and maintained by National Coordinator. All data entry will be reviewed for logical errors by the National Coordinator. Subsequent review of data will be done by CRO's staff (e.g., study data manager) and 100% of key variables will be double-checked for accuracy of data entry. The study statistician of MAH/MAH representative will also conduct reviews of the cumulative data from the study database for distributions and values that are illogical.

Property of the Sanofi Group - strictly confidential

Access to the database will be controlled by password, with different access privileges assigned to the data entry staff and administrative staff. These privileges will be outlined in detail in relevant operational documents. An audit log is built into the database to archive all such entry edits. Hard copies of patient files and signed informed consent forms will be kept in a locked cabinet by National Coordinator/involved HCP as appropriate.

Additional details regarding data collection and validation procedures will be detailed in appropriate operational documents

9.8.2 Data quality control at site level

Pregnancy outcomes reported by women enrolled in the study will be verified by HCPs responsible for the care of enrolled women and their infants through medical record review.

The methodology of data Quality Control and appropriate consecutive corrective actions will be detailed in the study manual.

9.9 LIMITATIONS OF THE RESEARCH METHODS

As reporting of pregnancies is totally voluntary, it is possible that even in prospectively reported cases, potential bias could exist.

The primary limitation of an international, prospective observational cohort study is selection bias (12). Women who voluntarily enroll may represent particularly high or low risk pregnancies, leading to potential over- or under-ascertainment of potential malformations and adverse pregnancy outcomes such as spontaneous abortion. The impact of selection bias can be minimized through robust outreach to recruit women exposed to LEMTRADA during their pregnancy, and efforts to retain all women who enroll into the study through the entire study follow-up period. Outreach strategies will include dissemination of information about the study and how to enroll through a variety of venues. Another potential limitation is that the calculation of fetal malformations will exclude information from spontaneous abortions, induced abortions, or fetal deaths where information on malformations was not available. For these excluded fetal losses, it is unknown what percentage would have resulted in potentially normal outcomes or malformations, leading to potential over or underestimation of malformation rates. The use of unexposed external comparison groups will also address these limitations to some extent.

Pregnancy outcome information is considered "lost to follow-up" if unobtainable after 4 attempts. It is possible that outcomes among pregnancies lost to follow-up could differ from those with documented outcomes. Because of differences in follow-up procedures across countries and individual reporting patterns, it is currently not possible to assess with any certainty what impact the potential biases the losses to follow-up may have on the analysis. However, efforts at comparing some of the characteristics of each group may be conducted in an attempt to address this potential source of bias.

The protocol also recognizes that some defects and other infant abnormalities may not be evident at birth and are often diagnosed during the first year of life. In this study, the infant is followed until one year of age. Requiring the Primary Analysis Population to have complete follow-up until one year of age raises the potential for lost to follow-up. Lost to follow-up must be minimized in this study, in particular, because pregnancy exposures are expected to be rare and accordingly, enrollment is expected to be difficult. A subgroup analysis will be conducted to estimate the rate of birth defects among infants with complete follow-up until one year of age.

While the study analysis is primarily limited to prospective reports, retrospective reports will be carefully reviewed and used to assist with signal detection and summarized separately in the final reports.

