9.6.5 Procedure for withdrawal of patients from study follow-up schedule

The HCPs and National Coordinators will endeavor to conduct follow-up in accordance with the protocol's study data collection schedule for all women enrolled in the study who are eligible, have provided informed consent, and have completed the initial enrolment interview. National Coordinator will make multiple attempts to contact patients via HCPs with valid contact information using multiple mechanisms (e.g., phone, fax, mail) before a woman is considered lost to follow-up. Women with missing pregnancy outcome information due to lost to follow-up will be described in study enrollment-related analyses but will be excluded from the denominator of outcome-related analyses.

Participation in the study is voluntary and women may withdraw consent to participate in follow-up visits at any time. For women who withdraw consent, study participation for both the woman and her infant will terminate immediately upon her request. Once a woman is withdrawn from the study, routine pharmacovigilance follow-up procedures will be applied for all ongoing adverse events.

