9.7 DATA ANALYSIS

9.7.1 Primary analysis

The primary analysis population will include all women enrolled in the study prospectively who meet the study inclusion criteria and have pregnancy outcome data recorded. Outcomes for the primary analysis population will primarily be compared with pregnancy outcomes in unexposed external comparison groups. Ascertainment of pregnancy outcomes will be considered completed when:

- Pregnancy outcome is known and was not a live birth, or
- Pregnancy outcome was a live birth and the 1-year post-delivery follow-up has been completed, or
- The woman has been classified as lost to follow-up, or
- The woman has withdrawn informed consent prior to ascertainment of pregnancy outcome.

Otherwise, the pregnancy outcome will be considered as pending.

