14 APPENDICES

Appendix A Description of pregnancy outcomes

Each defect will be categorized using the CDC MACDP classification of birth defects (CDC MACDP, 1998). Major defects identified from the point of conception up to 1 year of age will be included in the analysis. Defects identified in any live birth will be considered in the primary analysis. Defects identified in any stillbirths or abortions (spontaneous or induced) will be considered in secondary analyses.

MACDP defines major structural or genetic birth defects as conditions that

- 1. result from a malformation, deformation, or disruption in one or more parts of the body, a chromosomal abnormality, or a known clinical syndrome;
- 2. are present at birth;
- 3. have a serious, adverse effect on health, development, or functional ability.

A **minor** structural defect is defined as a defect which occurs in less than 4 percent of the population but which has neither cosmetic nor functional significance to the child (e.g., complete 2,3 syndactyly of the toes).

Spontaneous abortion

Any loss of a fetus due to natural causes at \leq 20 weeks gestation determined from the estimated date of conception or by ultrasound as spontaneous abortion. If available, information from gross or pathological examination of the abortus or fetus will be documented.

Induced abortion

Pregnancy termination is defined as any induced or voluntary fetal loss. If available, information from gross or pathological examinations will be documented.

Preterm birth

A live birth that occurs before 37 completed weeks of gestation determined from the estimated date of conception. Elective caesarian deliveries or inductions prior to 37 completed weeks will be analyzed separately.

Small for gestational age

Birth size (weight, length, or head circumference) ≤10th percentile for gender and gestational age using the NCHS pediatric growth curves for full term infants. Prenatal growth curves will be used for preterm infants.

Property of the Sanofi Group - strictly confidential

Stillbirth

Any non-deliberate foetal death at >20 weeks gestation as estimated based on the estimated date of conception or by ultrasound.

Lost to follow-up

Enrolled women will be considered lost to follow-up if they are eligible, have provided informed consent, and have completed the initial intake interview but pregnancy outcome information is not available within 1 year of the estimated delivery date despite 4 attempts to obtain this information.

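### The protocol gives conflicting rules for who is in the primary spontaneous-abortion denominator; its one-year follow-up requirement, if applied, would remove only non-events and raise the exposed rate

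*Protocol*

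**What the plan says.** - **Population.** Sections 9.2.3 and 9.7.1 admit prospective, eligible women with a recorded pregnancy outcome. The definition has no one-year condition.
- **Completion.** The same sections then list when ascertainment is complete. An outcome other than a live birth is complete once known. For live births the condition is "Pregnancy outcome was a live birth and the 1-year post-delivery follow-up has been completed, or". If no condition on the list is met, the rule is: "Otherwise, the pregnancy outcome will be considered as pending".
- **Limitations.** Section 9.9 states: "Requiring the Primary Analysis Population to have complete follow-up until one year of age raises the potential for lost to follow-up". The same paragraph ends by planning a subgroup analysis of birth defects in infants followed to one year.
- **Loss to follow-up.** Under section 9.6.5, women with missing pregnancy outcome because of loss to follow-up "will be excluded from the denominator of outcome-related analyses". Appendix A classes a woman as lost when "pregnancy outcome information is not available within 1 year of the estimated delivery date despite 4 attempts", so the definition turns on the pregnancy outcome and not on infant data.
- **Sample size.** Section 9.5.1 describes the 193 women as followed to one year, but the only deduction is for missing pregnancy outcome: "Assuming 5% drop out (outcome unavailable): 204*95%=193 patients".
- **Endpoint.** SAB is the primary outcome. Appendix A limits it to losses at 20 weeks or earlier.

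**The concern.** SAB status is settled at 20 weeks, and nothing learned about the infant at one year can change it. A completeness rule that bears only on live births therefore deletes only non-events from the SAB denominator.

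The text leaves it open whether such a rule applies. A live birth recorded at delivery but without the 1-year contact meets the population definition, fails the completion rule, is not lost to follow-up under Appendix A, and fails the requirement described in section 9.9. No section says how pending women are analysed. Two analysts following the protocol could report different primary SAB rates, and the choice could be made after the data are seen.

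A second, smaller issue does not depend on that ambiguity. A woman still pregnant at the third-trimester interview (26 to 32 weeks, Table 2) is known not to have had an SAB. If she is then lost, section 9.6.5 still removes her from the denominator.

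**Working it through.** **Inputs from section 9.5.** There are 193 exposed women (204 × 0.95 = 193.8) and 117 comparators (125 × 0.96 × 0.98 = 117.6). The background SAB rate is 13.5%, the target relative risk (RR) is 2.0, and live births are 80% of outcomes. The test is Fisher's exact, specified as "at 80% power and a 1-sided two-sample test with significance level of 0.025".

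**The plan's own figure.** Full enumeration of the one-sided Fisher test at 27.0% against 13.5%, with 193 and 117 women, gives 78.1% power. A pooled z-test gives 81.3%. Both agree with the stated 80% to within two points. With no true effect and no exclusions, the Fisher test rejects in 1.7% of cases.

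**One-year rule applied to the exposed group only.** Let m be the share of live births without 1-year data. The documents give no value, so 0 to 30% is an assumed range. The share of women kept is d = 1 − 0.80m. The observed rate is 0.135/d, the apparent RR under no true effect is 1/d, and the exposed number is 193d.

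| m | d | Exposed n | Observed SAB | Apparent RR | Fisher false-positive rate |
|---|---|---|---|---|---|
| 0% | 1.00 | 193 | 13.5% | 1.00 | 1.7% |
| 5% | 0.96 | 185 | 14.1% | 1.04 | 2.3% |
| 10% | 0.92 | 178 | 14.7% | 1.09 | 3.1% |
| 20% | 0.84 | 162 | 16.1% | 1.19 | 6.1% |
| 30% | 0.76 | 147 | 17.8% | 1.32 | 11.8% |

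The apparent RR is 1/d whatever the background rate, as long as live births stay at 80%. It therefore also applies at the 11.5%, 16.6% and 19.5% listed in Table 1.

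**Same rule in both groups.** If comparators lose the same share, both rates are divided by the same d and the RR returns to 1.00. The false-positive rate is then 1.6% to 1.7% for m from 10% to 30%. Both absolute SAB rates remain inflated.

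**Women lost after 20 weeks.** The extreme case is that all of the planned 5% loss falls after week 20.

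- Exposed rate: 0.135/0.95 = 14.2%, against 13.5%.
- If the comparator's 4% missing data (section 9.5.2) arises and is dropped in the same way: 0.135/0.96 = 14.1%, so RR = 0.96/0.95 = 1.01, with a false-positive rate of 1.8%.
- If only the exposed group is affected: RR = 1/0.95 = 1.05, with a false-positive rate of 2.5%.

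**The case against.** The strongest defence is that the operative definition already keeps these live births. Sections 9.2.3 and 9.7.1 ask only for a recorded pregnancy outcome, and a live birth recorded at the interview within six weeks of the end of pregnancy has one. The completion list looks like a case-closure rule rather than a membership rule: it counts lost and withdrawn women as complete, yet lost women with missing outcomes are removed from outcome denominators. Complete therefore cannot mean included, and pending need not mean excluded. The section 9.9 sentence sits in a paragraph about infant defects diagnosed late, and its subgroup of one-year completers presupposes a wider primary population.

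This stands against a stronger reading that a reader might infer, namely that the primary population drops live births without 1-year data and so inflates the exposed SAB rate. The documents do not settle that. It does not remove the contradiction, because section 9.9 describes the one-year condition as a requirement on that named population.

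Four further objections also hold in part.

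- The 10% to 30% range is assumed. The protocol plans for 5% missing outcomes, and at 5% missing 1-year data the false-positive rate stays below the nominal 2.5%.
- The documents do not say whether the comparator cohorts face a one-year rule, so bias in the RR is conditional.
- Section 9.6.5 also removes women lost before 20 weeks, some of whom may have had an SAB. The net direction of all losses to follow-up is therefore uncertain, and section 9.9 acknowledges that their impact cannot be assessed.
- The supportive left-truncated Kaplan-Meier analysis in section 9.7.5 can censor lost women, but it is not the main criterion.

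**Conclusion.** The finding is an unreconciled contradiction over the primary denominator, not a settled exclusion. If the one-year requirement in section 9.9 is followed, the exposed SAB rate can only rise, because every woman removed is a non-event. The RR and false-positive figures for 10% to 30% missing rest on three assumptions: that level of missing 1-year data, 80% live births, and comparators not held to the rule. At 5% missing the effect is small, and with the same rule in both groups the RR is unbiased. The documents therefore do not support saying that the plan will produce a false safety signal.

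The exclusion of women lost after 20 weeks is stated text but minor: at most 14.2% against 13.5% at the planned 5% loss, and an RR of about 1.01 if comparators are handled alike.

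The point still needs correcting. It concerns the primary endpoint, and the protocol as written allows more than one denominator.

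**What to change.** Reconcile sections 9.2.3, 9.5.1, 9.6.5, 9.7.1 and 9.9 as follows.

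1. State that SAB, and every other outcome settled by delivery, counts live births at delivery whatever their 1-year status.
2. Count women documented as still pregnant after 20 weeks as having no SAB, and apply the same rule in the patient-level comparator cohorts where the data allow.
3. Apply one-year completeness to infant outcomes only. Delete or correct the section 9.9 sentence that ties the primary population to it, and say what pending means for analysis.
4. In section 9.5.1, say whether the 193 are women with a known pregnancy outcome or women followed to one year.
5. Leave censoring of women lost before 20 weeks to the supportive Kaplan-Meier analysis. Censoring does not fit the planned binary RR and Fisher comparison.

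The cost is protocol and SAP wording, with no new data from exposed women. The downside is a small asymmetry, lowering the exposed rate relative to the comparator, if gestational age at last contact is not available for the comparator cohorts. In that case, report the SAB rate with and without the late-lost women.
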